A cost-consequence analysis is a form of economic evaluation where costs and outcomes are presented in a disaggregated fashion and it can be used to highlight the trade-offs involved in a decision to more widely adopt ECP. The approach is recommended when evaluating technologies whose mechanism of action and outcomes are complex, but it can also be of use when considering any health technology.

A cost-effectiveness analysis is a form of economic evaluation where the effects of an intervention are combined with costs to produce an incremental cost-effectiveness ratio. In the analysis we will conduct we will combine the impacts on quality of life, morbidity, harms and survival into a single measure, the quality adjusted life year (QALY). Results are presented as the extra cost incurred for the more costly (but more effective technology) to produce one more QALY. This is more commonly presented as the incremental cost per QALY gained. This form of economic evaluation is the main form of economic evaluation used by health care decision-makers and regulators throughout the world.

Methods

Comparators

These will match the intervention and control groups of the E-CLAD UK. Namely, ECP plus standard of care (SOC) versus SOC alone in the treatment of CLAD.

Target population

Adults, 16 years or over who have received a double (bilateral) lung or heart and bilateral lung transplantation that fulfil the ISHLT diagnostic criteria for Chronic Lung Allograft Dysfunction. All participants will need to meet the inclusion criteria of E-CLAD UK.

Cost perspective

Costs will be measured with the perspective of UK National Health Service (NHS) & Personal Social Services (PSS).

Time Horizon

24 weeks, matching the trial follow-up of E-CLAD UK.

Cost Analysis

A cost analysis will be conducted of ECP compared to no ECP over the 24 weeks of the E-CLAD UK trial. Costs will include the cost of delivering the ECP, and impacts on subsequent care (e.g. consultations and hospital admissions) over the 24 week follow-up period.

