The costs of the ECP delivery will involve a planned 9 sessions (18 treatments) over a 24-week period. The cost estimates will be derived for a centre level, which is what will be the cost of a centre adopting ECP. The resources used in delivering ECP compared to no use of EP will be based on a microcosting exercise. The microcosting exercise will involve identifying, measuring and costing the use of staff time recorded by job title involved in all aspects of the delivery of the EP, the use of other hospital resources associated with receiving ECP, and ECP hardware and disposables.

Data on use of secondary health care services over the 24-week follow-up period will be captured on an electronic case report form by a research nurse for each trial participant. These data will be combined with unit cost data taken from routine sources, e.g. NHS reference costs.

For each trial participant a total cost over the 24-week follow-up period will be estimated. From this the difference in mean costs between trial arms will be calculated. We will adjust for the range of factors that have been specified as part of an 'adjusted analysis' in the statistical analysis plan for E-CLAD UK to ensure comparability between outcomes.

Cost-consequence analysis

The cost of ECP and of subsequent care for patients compared with no ECP will be presented alongside the trial outcomes from the E-CLAD UK in the form of a cost-consequence analysis. How costs will be derived is presented above and consequences will be related to the headline results of the safety and efficacy analysis conducted in E-CLAD UK.

Cost-effectiveness analysis

For this analysis, QALYs will be estimated over the trial duration based upon responses to the EQ-5D-5L questionnaire. The EQ-5D-5L is being collected at baseline and 24 weeks in the NIHR E-CLAD UK trial.¹ The responses to the EQ-5D-5L at both time points will be converted into health state utility values and QALYs estimated for each trial participant using the area under the curve approach. There is no currently accepted value set for EQ-5D-5L in the UK although one is in development. If an approved value set is developed before this analysis is conducted then this will be used to derive

EQ-5D-5L utility values at baseline and 24 weeks. If not, the EQ-5D-3L index values at baseline and 24 weeks will be estimated using the cross-walk value set², as recommended by NICE.³

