A focussed search of literature will be conducted to identify studies investigating survival for different levels of decline in lung function. For example, Kneidinger *et al.*⁴ report a hazard ratio for a $\leq 10\%$ decline to total lung capacity (TLC) compared to $>10\%$ decline in TLC, and Mason *et al.*⁵ report survival data for FEV1 levels post-transplant. Survival evidence will be used to model survival within a Markov model.

To model quality of life beyond 24 weeks, we will search for evidence of decline in lung function over time and consult clinical experts on how this relates to changes in quality of life. For example, Mason *et al.*⁶ and Sithamparanathan *et al.*⁷ report decline in FEV1 over time. We will also reanalyse data from the E-CLAD UK trial to explore the relationship between the change in rate of decline in FEV1 (a secondary outcome in the E-CLAD UK Trial) with changes in EQ-5D-5L utility values also estimated as part of the E-CLAD UK trial will also provide evidence for the decline in FEV1 for patients receiving ECP and receiving standard of care.

Cost data will come from the Cost analysis described above but we will also reanalyse data from the E-CLAD UK trial to explore the relationship between the rate of decline in FEV1 with total cost at the end of the trial follow-up period. In addition, clinical experts will be consulted on healthcare resource use incurred beyond 24 weeks. These data will be used to assign costs to each element of the Markov model.

Once probabilities, utilities and costs (the model parameters) have been assigned to the Markov model the model will be rolled back to estimate average total costs, life years and QALYs for both EP compared to the non-use of ECP. From these the incremental cost per QALY gained over a life-time long time horizon will be estimated.

[figure not shown]
Following best practice recommendations we will assign each model parameter a statistical distribution to reflect the imprecision in estimates. In a probabilistic sensitivity analysis we will use Monte Carlo Simulation methods to estimate credible intervals surrounding the difference in QALY and the difference in costs. We will also present the imprecision surrounding estimates of cost-effectiveness.

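### Appendix 3 relates FEV1 decline to a total cost that includes ECP delivery, so this input to the lifetime model would understate the care saving from stabilisation if ECP works

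*Protocol*

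**What the plan says.** Appendix 3 Part 1 (Cost Analysis) sets the content of trial cost: "Costs will include the cost of delivering the ECP, and impacts on subsequent care". Delivery is costed for a "planned 9 sessions (18 treatments) over a 24-week period". Then: "For each trial participant a total cost over the 24-week follow-up period will be estimated". The next step is between arms: "From this the difference in mean costs between trial arms will be calculated". The covariate adjustment described there belongs to that comparison.

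Part 2 (Method) names three sources for the model's costs:

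- Part 1 and a reanalysis of trial data: "Cost data will come from the Cost analysis described above but we will also reanalyse data from the E-CLAD UK trial". The stated purpose of the reanalysis is to "explore the relationship between the rate of decline in FEV1 with total cost at the end of the trial follow-up period".
- Experts: "clinical experts will be consulted on healthcare resource use incurred beyond 24 weeks".

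It then says: "These data will be used to assign costs to each element of the Markov model".

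Nothing in Part 2 removes ECP delivery from the total, fits the relationship within arm, or adds an arm term. The sensitivity analyses at the end of Part 2 take ECP to stop at 24 weeks.

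**The concern.** A health-state cost should describe what care costs for a patient at a given lung function. ECP delivery cost is not of that kind, because randomisation sets it. The trial also expects the arm that carries this cost to decline less, so slow decline and high total cost go together through allocation.

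A second link can arise inside the ECP arm. Section 5.12 ends trial ECP on withdrawal, and Section 5.5.1 puts the formal response assessment after 6 of 9 cycles. A participant who leaves for progression may therefore have a smaller ECP cost than one who stabilises.

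Both links push the same way. If the relationship is carried into the model, the stable state absorbs part of the cost of a treatment that has ended. If ECP is also charged as a treatment, part of it is counted twice. If the same state costs serve both strategies, part of it falls on the strategy without ECP. Each of these distorts the lifetime cost per QALY.

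**Working it through.** The protocol gives no prices and no figure for this relationship, so there is nothing to reproduce. The bias can be expressed in units of an ECP course cost.

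**Inputs**
- Response 55% (ECP) and 30% (SOC), 1:1 allocation: Section 10.1.
- 9 planned cycles, 6 given before the 12-week assessment: Section 5.5.1.
- C = cost of a full course; S = true extra non-ECP care cost of a non-responder over a responder. Neither is given.
- q = share of ECP-arm non-responders who stop at 6 cycles (assumption, 0 to 1). The mean share of the course they receive is f = 1 − q/3.
- ECP-arm responders are taken to receive all 9 cycles, and no rescue cost is included.

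**Step 1: who carries the ECP cost**
- P(ECP | responder) = 0.55/(0.55 + 0.30) = 0.647
- P(ECP | non-responder) = 0.45/(0.45 + 0.70) = 0.391

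**Step 2: unadjusted difference in total cost, responder minus non-responder**

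Difference = −S + C(0.647 − 0.391f). The correct answer is −S.

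| q | f | ECP term | Sign changes if C/S exceeds |
|---|---|---|---|
| 0 | 1.000 | +0.256C | 3.9 |
| 0.5 | 0.833 | +0.321C | 3.1 |
| 1 | 0.667 | +0.386C | 2.6 |

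**Step 3: share of the true saving that is recovered**

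Share = 1 − (ECP term/C) × r, with r = C/S assumed, for q = 0 and q = 1:
- r = 1: 74% and 61%
- r = 2: 49% and 23%
- r = 4: −2% and −54%

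**Step 4: continuous FEV1 loss**

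With normally distributed loss set to give 55% and 30% response, simulation puts the ECP-induced slope per 10 points more loss at −0.147C, −0.098C and −0.074C for an assumed SD of 10, 15 and 20 points. The direction is the same.

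**Step 5: if ECP has no effect on response**

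Both probabilities in Step 1 become 0.5 and the term is 0.5C(1 − f): 0 at q = 0, 0.083C at q = 0.5 and 0.167C at q = 1. Only the early-stopping part remains.

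**Step 6: candidate remedies**
- Arm covariate alone: residual = (1 − f)C × w, where w = 0.55×0.45/(0.55×0.45 + 0.30×0.70) = 0.2475/0.4575 = 0.541. This gives 0 at q = 0, 0.09C at q = 0.5 and 0.18C at q = 1.
- ECP delivery left out of the cost: the ECP term is 0 for every q.

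**The case against.** The strongest reply is that this is an outline of a separately funded and separately reported evaluation (Section 2.3.3), and that the relationship is only to be explored. The Part 1 cost analysis is named first, and experts are the stated source for resource use after 24 weeks. A reader might infer that all the model's costs rest on this relationship; Part 2 does not say that. Nor does it say that the fit is pooled across arms or unadjusted, so the figures above apply to the plainest reading of the text.

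The protocol also treats ECP as separable. Delivery is microcosted apart from secondary care recorded on the eCRF, and the planned threshold analysis of further ECP for responders needs a distinct ECP cost.

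Some costs would run the other way. Non-responders are eligible for rescue treatment (Section 5.5.3), withdrawn participants are asked to allow use of routine data (Sections 5.11 and 5.12), and Appendix 1 lists total lymphoid irradiation, and ECP for those not given it in the trial, among the rescue options. If captured, these costs fall on decliners.

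The 0.39 figure is an extreme. Sections 1.3 and 5.4.5 let week-12 non-responders continue ECP, and Section 7.3 also counts as non-responders those with more than 10% loss at 24 weeks, many of whom could have had all 9 cycles.

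All of this limits the weight and certainty of the bias. It does not change the fact that Part 2 names total cost as the variable and that Part 1 puts ECP delivery inside it. That is an unsuitable variable stated in the text, not a detail left for later.

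**Conclusion.** The point holds as a fault in one of three inputs to the lifetime model's costs. At the planned response rates, an unadjusted relationship makes a responder look dearer by 0.26 of an ECP course cost with full completion, rising toward 0.39 at the extreme. The between-arm part requires ECP to slow decline as planned. The size assumes that care cost depends only on response and that rescue costs are not counted.

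Two stronger readings are tempting and not supported. One is that the state costs would come out reversed. That needs a course to cost more than about 2.6 to 3.9 times the true extra care cost of a non-responder, and the protocol gives neither price. The other is that early deaths make the steepest decliners look cheap. Nothing in the protocol shows this, and admissions before death could raise their totals.

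The consequence is confined to the economic model; the efficacy and safety analyses are not touched. The wording should still be corrected, because the named variable is wrong for its purpose.

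**What to change.** In Appendix 3 Part 2 (Method), replace total cost, as the variable related to FEV1 decline, with care cost excluding ECP delivery, preferably with trial arm as a covariate. State that ECP delivery enters the model as a separate cost, in the ECP strategy only, for the weeks it is given. An arm covariate on total cost would not be enough, since a residual remains if non-responders stop ECP early. It would also help to say whether rescue-treatment costs after withdrawal are counted.

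The cost is a sentence or two in the appendix or the health economics plan. No new data are needed, because Part 1 already builds ECP cost by microcosting, apart from the eCRF resource use.

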16.4 Appendix 4 - Safety Reporting Diagram

[figure not shown]

Contact details for reporting SAEs and SUSARs

Please send SAEs form(s) via [contact]

Please ensure that no participant identifiable information is included within the SAE form

16.5 Appendix 5 – Non Responder Decision Tree

16.6 Appendix 6 - Amendment History

Amendment Number	Protocol version no.	Date issued	Author(s) of changes	Details of changes made
